## JHM IRB - eForm A – Protocol

### Anxiety in Parkinson's: Use of quantitative methods to guide rational treatment

#### 1. Abstract

- a. Provide no more than a one-page research abstract briefly stating the problem, the research hypothesis, and the importance of the research.

Anxiety in PD aggravates physical disability and independently contributes to poor health-related quality of life. Clinically significant anxiety occurs in up to 40% of patients with PD, a markedly higher prevalence than healthy or comparably disabled persons without PD. Anxiety in PD is complicated by atypical presentations, comorbidity with depression, and phenomenological overlap with other non-motor and motor symptoms of PD. As a result, anxiety syndromes in PD are often poorly characterized. In my previous work, 22% of anxious patients with PD had clinically significant anxiety syndromes that failed to meet criteria for the established Diagnostic and Statistical Manual (DSM) anxiety diagnoses. These 'non-DSM' anxiety syndromes were often associated with fluctuations in motor symptoms resulting from the 'wearing-off' of dopamine based treatments. However, even when anxiety occurs in association with motor fluctuations, it is not clear whether it is a reaction to the change in motor function and dopamine levels or an independent process. In order to better target and treat anxiety syndromes in PD the relationship between PD-specific features and anxiety needs to be better understood.

There have been no randomized controlled drug trials to treat anxiety in PD. Current management strategies are based on expert opinion and observational studies and recommend the anti-anxiety treatments typically used in the non-PD population. Yet, many of these anti-anxiety treatments may worsen motor function and increase fall risk in PD. Currently, there is no evidence-based standard to guide the pharmacologic treatment of anxiety in PD. The overlap between PD-specific features and anxiety suggests that certain anxiety syndromes may emerge from the neurodegenerative process of PD. The goal of this study is to, 1) investigate a system of classification for anxiety disorders that accounts for patterns of comorbidity with PD-specific features (e.g. wearing-off) and 2) to design and conduct an intervention that tests whether treating fluctuations in dopaminergic neurotransmission improves anxiety in an 8-week study of rotigotine vs. placebo.

#### 2. Objectives (include all primary and secondary objectives)

- (1) **Using latent class analysis, investigate whether a hypodopaminergic state, produced by a temporary interruption of dopamine medications, is associated with a distinct anxiety syndrome in PD in a cross-sectional study of 200 subjects with idiopathic PD. Hypothesis: Certain anxiety syndromes and PD have a shared causal mechanism. Demonstrating that certain anxiety symptoms are associated with motor fluctuations, that is both anxiety and motor fluctuations are increased in hypodopaminergic states and cluster together based on a latent variable will support this hypothesis**

(2) **Conduct an 8-week intervention study of rotigotine (n=30) compared to placebo (n=30) for the treatment of anxiety disorders in PD that will provide estimates of effect size and the impact of co-occurring motor fluctuations on the treatment of anxiety. Hypothesis: Treatment with rotigotine for anxiety associated with motor fluctuations will result in a greater reduction of anxiety as compared to treatment with placebo**

3. **Background** (briefly describe pre-clinical and clinical data, current experience with procedures, drug or device, and any other relevant information to justify the research)

Anxiety is common in PD and associated with motor fluctuations. Anxiety is one of the most common non-motor symptoms in PD, occurring in up to 56% of patients, often in association with PD-specific features.(1,2) Anxiety syndromes are more prevalent than in healthy or comparably disabled individuals without PD and result in greater disability and a lower quality of life.(3-6) Anxiety syndromes in PD are a heterogeneous group of conditions that are characterized by either episodic or persistent anxiety phenomena, frequent comorbidity with depression, and atypical presentations when compared to anxiety syndromes in the general population.(7-9) In a previous study, we found that 22% of PD patients had atypical anxiety syndromes not specifically described by the *Diagnostic and Statistical Manual of Mental Disorders*, 4th edition, Text Revision (DSM-IVTR).(10) The most common atypical presentation of anxiety in PD in our study and others is when anxiety occurs as an episodic symptom potentially related to the wearing-off of dopaminergic treatment and motor fluctuations.(3,10,11) "Wearing-off" is defined as a generally predictable recurrence of motor and non-motor symptoms as the effect of dopaminergic treatment declines over a given dose.(12) The loss of treatment effect leads to episodic reemergence or worsening of motor and non-motor symptoms typically referred to as "fluctuations". The pathophysiology of wearingoff is thought to be related to the progressive loss of dopamine in PD.(13) Wearing-off occurs in up to 40% of PD patients within 4-6 years of starting levodopa therapy, although it has also been reported to occur much earlier, within 5-6 months, in up to 30% of patients.(14,15) Other studies suggest that anxiety (and depression) may be a 'phenocopy' of autonomic dysfunction, another common non-motor symptom, and not associated with fluctuations or wearing-off of dopaminergic medications.(16) Whether wearing-off anxiety, autonomic dysfunction related anxiety, and other subtypes are specific to PD and represent subgroups with distinct etiologies and treatment is not known.

There are very few data on treatment of anxiety in PD. A recent study by the MDS non-motor task force concluded there are insufficient data on the treatment of anxiety in PD to establish evidencebased treatment standards. (17) Anxiety is associated with worse quality of life, greater motor impairment, more dyskinesias, and a greater frequency of motor fluctuations.(18,19) In a recent study, our data showed that anxiety associated with motor fluctuations was an independent predictor of lower self-perceived health status in PD.(10) Despite the distress and dysfunction caused by anxiety syndromes and their unusually high prevalence in PD there are no randomized controlled trials (RCTs) on which to establish evidence-based treatment. (17) In addition, many conventional anxiety treatments can be problematic when used in PD. Benzodiazepines and tricyclic antidepressants can increase the risk of falls and contribute to the risk of delirium and confusion in PD.(20,21) Even selective serotonin reuptake inhibitors(SSRIs), which are typically well tolerated in the general population, may worsen tremor and other motor symptoms in PD.(21,22) Therefore, a RCT of a non-traditional anti-anxiety agent that takes into account the potential association between anxiety and PD-related features, and a potential PD-specific vulnerability to side-effects is needed.

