#### 4. Study Procedures

- a. Study design, including the sequence and timing of study procedures (distinguish research procedures from those that are part of routine care).

For objective 1: Subjects will be assessed in both the “on” and “off” motor states following the clinical protocol from the Core Assessment Program for Surgical Interventional Therapies in PD (CAPSIT-PD).(23) We use the CAPSIT-PD protocol routinely in the PDRC and movement disorder clinics and will include consenting individuals as part of this study. However, a portion of the subjects recruited will have the CAPSIT-PD protocol exclusively for this study and not as a part of routine clinical care. "Wearing-off" and the "off-motor state" in PD are defined as a generally predictable recurrence of motor and non-motor symptoms as the effect of dopaminergic medications stops.(12) Subjects will temporarily stop all dopaminergic medications for a minimum of 12-hours in order to be assessed in the “off” motor state in the morning. (Most individuals with PD do not take medications overnight and usually take their last dose between 5-9pm. Therefore most participants will only be off medications for a few hours more than they normally would be as the study will be conducted in the morning) The on- and off-state assessments are listed below. Subjects will then take their usual morning dopaminergic medications and after one hour, to allow them to return to their best "on" state, repeat the CAPSIT-PD on-off battery. In addition to the on-off testing battery, several PD-related clinical features will be assessed, only in the on-state, using instruments recommended by the National Institute of Neurological Disorders and Stroke Common Data Element Project (NINDS-CDE)(24) for PD.

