##### CAPSIT-PD on- and off-state testing battery

Each assessment will be conducted twice, once in the off-state and once after resuming PD meds in the on-state

1. Anxiety: Hamilton Anxiety Rating Scale (HAM-A)(25)
2. Depression: 17-item Hamilton Depression Rating Scale (HAM-D)(26)
3. Motor and non-motor fluctuations: 19-symptom wearing-off questionnaire (WOQ-19)(27)
4. Physical Disability: Schwab and England Scale (SE)(28)
5. Motor symptom severity: MDS-UPDRS part III(30)
6. Symbol Digit Modalities Test(45)
7. Stroop Color and Word Test(46)

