## 7. Study Statistics

- a. Primary outcome variable. Hamilton Anxiety Rating Scale(HAM-A)
- b. Secondary outcome variables. 17-item Hamilton Depression Rating Scale (HAM-D), 19symptom wearing-off questionnaire (WOQ-19), Schwab and England Scale (SE), MDS-UPDRS part III
- c. Statistical plan including sample size (n=200) justification and interim data analysis.  
For objective 1: We will conduct a latent profile analysis (LPA) using the following observed variables (measured in the on-state) as latent profile indicators: age of PD onset, LEDD, HAMA, HAM-D, WOQ-19, SE, UPDRS part III, and MoCA score, to model unobserved (i.e. latent) profiles. LPA is a type of latent class analysis that uses continuous indicator variables. Using LPA we will determine 1) the number of classes/profiles that best fits symptom profiles of observed values, 2) the proportion of the sample that belongs in each class/profile (e.g. class prevalences), and 3) the means of each latent profile, conditioned upon membership in each class. We will then test whether specific subject characteristics (age, gender, variability of symptoms between on- and off-states (as change scores), and motor fluctuations), from the battery above predict differential membership in the identified latent profiles via latent profile regression. With latent profile regression, predictors of latent profile membership are modeled via multinomial logistic regression. Statistical power for latent profile regression was determined via monte carlo simulation,(42) assuming 3 classes/profiles with prevalences of 30%, 10%, and 60%. We would have 80% or greater power to detect a log odds ratio for an association between a standardized predictor and latent profile membership of 1.17 for profile 1 (prevalence of 30%) and 1.71 for profile 2 (prevalence of 10%), with profile 3 as the reference class. Antidepressant, anti-anxiety, and other psychiatric medication use will be controlled for in the analysis.

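### Objective 1's criterion for supporting a shared causal mechanism is also predicted by anxiety that is only a reaction to motor worsening, and no planned analysis separates the two

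*Combined protocol and SAP*

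**What the plan says.** Section 2, objective 1, states a causal hypothesis: "Certain anxiety syndromes and PD have a shared causal mechanism". It then says what would count in its favour: "Demonstrating that certain anxiety symptoms are associated with motor fluctuations, that is both anxiety and motor fluctuations are increased in hypodopaminergic states", and that the two "cluster together based on a latent variable will support this hypothesis". The setting is given as "in a cross-sectional study of 200 subjects with idiopathic PD".

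Section 4 supplies the contrast between states. Dopaminergic medication is interrupted for at least 12 hours and the subject is rated. "Subjects will then take their usual morning dopaminergic medications and after one hour" the battery is repeated. For that battery, "Each assessment will be conducted twice, once in the off-state and once after resuming PD meds in the on-state". It includes the HAM-A, the wearing-off questionnaire (WOQ-19), Schwab and England (SE) and MDS-UPDRS part III.

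Section 7c fits a latent profile analysis to eight on-state indicators, with HAM-A, WOQ-19, SE and UPDRS III entered side by side. Profile membership is then regressed on age, gender, "variability of symptoms between on- and off-states (as change scores), and motor fluctuations". The only other adjustment named is for psychiatric medication.

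The Abstract describes the open question about anxiety that accompanies motor fluctuations: "it is not clear whether it is a reaction to the change in motor function and dopamine levels or an independent process".

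**The concern.** The objective 1 criterion is one of co-occurrence: anxiety and motor state both worsen off medication, and they group together. Two causal structures predict this.

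- **Shared cause.** The loss of dopaminergic effect worsens movement and, separately, raises anxiety.
- **Reaction.** The loss of dopaminergic effect worsens movement, and the worse movement makes the patient anxious.

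A finding that is about equally likely under both cannot move a reader from one towards the other. What is at stake is the mechanistic conclusion of objective 1. If the criterion is met, the text licenses a statement of support for a shared mechanism that would read the same if anxiety were purely a response to immobility. The randomised comparison in objective 2 and participant safety are not affected.

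**Working it through.** **1. What the planned analyses can show.**

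| Element of the plan | Shared cause predicts | Reaction predicts |
|---|---|---|
| HAM-A higher off than on | yes | yes |
| UPDRS III and fluctuations worse off than on | yes | yes |
| Anxiety and motor measures grouping in profiles | yes | yes |
| Larger anxiety and motor change scores in the fluctuating profile | yes | yes |
| HAM-A change given motor change | may differ | may differ |

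Only the last row could separate the two, and section 7c does not plan it. There, change scores predict profile membership; HAM-A change is never an outcome with motor change as a covariate. Both change together with one medication interruption, rated once off and once on.

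**2. Algebra.** Let D be the dopaminergic drop, M = D + error the motor worsening and A the anxiety change.
- Shared cause: A = bD + error, so cov(M, A) = b·Var(D).
- Reaction: A = cM + error, so cov(M, A) = c·Var(M).

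Setting c = b·Var(D)/Var(M) makes the covariances equal; a shift in the mean and the residual variance can then be chosen so that the mean and variance of A also match.

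**3. Numerical illustration.** The documents give only n = 200; every effect size here is an assumption. I took 30% fluctuators with a drop 1 unit larger, other variance of D 0.25 and motor error variance 0.36.
- Var(D) = 0.25 + 0.3 × 0.7 = 0.46; Var(M) = 0.46 + 0.36 = 0.82.
- For b = 0.5: cov = 0.5 × 0.46 = 0.23; c = 0.23/0.82 = 0.28; Var(A) = 0.25 × 0.46 + 0.36 = 0.475; correlation = 0.23/√(0.82 × 0.475) = 0.37.

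The criterion was scored as met when all of these held: A and M each above zero off versus on (p < 0.05); two profiles preferred to one by BIC; and, in the fluctuating profile, higher anxiety and an anxiety change that differed from the other profile at p < 0.05. As a simplification, profiles used four indicators (WOQ-19, HAM-A, UPDRS III, SE) generated from the change scores. There were 400 runs per cell.

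| b | Correlation of M and A | Met, shared cause | Met, reaction only | Ratio |
|---|---|---|---|---|
| 0.3 | 0.24 | 77% | 75% (0.745) | 0.770/0.745 = 1.03 |
| 0.5 | 0.37 | 99% (0.992) | 97% (0.965) | 0.992/0.965 = 1.03 |
| 0.8 | 0.50 | 100% | 100% | 1.00 |

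With reaction only and no shift in the mean, so that zero motor change implies zero mean anxiety change, the figures were 77%, 98% and 100%.

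**4. How far an added regression could go.** I simulated HAM-A change on levodopa-equivalent dose (LEDD), adjusted for UPDRS III change. Assumptions: n = 200; standardised drop X; motor change 1 + 0.5X with residual SD 0.87; anxiety change 0.4 + 0.3X (shared cause) or 0.4 × motor change (reaction), residual SD 0.9; UPDRS III reliability 0.9 unless stated. Share of runs with the LEDD coefficient significant at 0.05:
- Shared cause, LEDD exactly equal to the drop: about 98%.
- Shared cause, LEDD correlated 0.7, 0.5 or 0.3 with the drop: about 75%, 44% and 20%.
- Reaction only: about 5% to 10% as UPDRS III reliability falls from 0.95 to 0.8.
- No direct dose effect, but severity correlated 0.5 with LEDD and acting on HAM-A change by 0.1, 0.2 or 0.3 outside UPDRS III: about 17%, 37% and 64%.

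The regression is informative in the favourable case only. It can miss a true shared cause and can signal one that is absent, so it cannot serve as a decision rule.

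**The case against.** The best defence is that the objective promises support and not proof, that its leading question is whether the off state is associated with a distinct anxiety syndrome, and that the stated aim is classification. The off/on comparison does bear on something real: anxiety unrelated to dopaminergic state should not rise when medication is withheld. All of that stands, and it limits the point. It does not remove it, because the hypothesis sentence is causal and the criterion attached to it does not favour that hypothesis over a motor reaction.

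Three stronger readings are tempting and are not supported.

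- A reader might infer that the study cannot separate the two explanations the Abstract calls unresolved. The Abstract's first arm covers a reaction to motor function and to dopamine levels, against an independent process. A motor reaction and a direct dopaminergic effect can both sit in that first arm, and the off/on contrast can inform the choice between arms. The gap is between reaction and shared mechanism, which is a different pair.
- A reader might infer that the criterion is met more readily under reaction than under a shared cause. That depends entirely on the path strengths assumed; once the motor-anxiety covariance is matched, the rates are nearly equal.
- A reader might infer that a positive objective 1 would be used to justify dopaminergic treatment of anxiety. The documents do not make objective 2 conditional on objective 1. Objective 2 is a double-blind randomised comparison that admits all anxiety subtypes (Table 2) and supplies its own data for the decision on a further trial (section 7c).

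**Conclusion.** The point holds in limited form. Meeting the objective 1 criterion supports an association of anxiety with the hypodopaminergic state and can count against anxiety unrelated to that state. It does not favour a shared causal mechanism over a reaction to motor worsening: the likelihood ratio was 1.00 to 1.03 in the matched simulation. That conclusion rests on the logic of the two structures; the percentages only illustrate it, and none of the effect sizes comes from the documents.

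The limitation applies to the study as planned. Paired off and on ratings of anxiety and motor state will exist, so a supportive analysis is possible. It would remain supportive, because only medication state is manipulated and the result depends on untestable assumptions about confounding and measurement error. The change is worth making because it alters what objective 1 can conclude.

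**What to change.** 1. **Reword objective 1 (section 2).** State that a positive result supports an association of the anxiety syndrome with the hypodopaminergic state, and that it is compatible with either a shared mechanism or a reaction to motor worsening.

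2. **Add one supportive analysis to section 7c, labelled as not a decision rule.** Regress the off-minus-on HAM-A change without and then with adjustment for the off-minus-on changes in UPDRS III and SE. Report the mean HAM-A change before adjustment and the change expected at zero motor change after it. LEDD may be added as an optional, imperfect proxy for the dose withheld.

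3. **State the limits with it.** Measurement error in UPDRS III leaves some association unadjusted, disease severity may confound, and LEDD is only a proxy. Report a null adjusted result as not distinguishing the explanations, and not as evidence for reaction.

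The cost is a sentence in the objectives, one regression on data already collected, and a more modest claim.

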#### 4. Study Procedures

- a. Study design, including the sequence and timing of study procedures (distinguish research procedures from those that are part of routine care).

For objective 1: Subjects will be assessed in both the “on” and “off” motor states following the clinical protocol from the Core Assessment Program for Surgical Interventional Therapies in PD (CAPSIT-PD).(23) We use the CAPSIT-PD protocol routinely in the PDRC and movement disorder clinics and will include consenting individuals as part of this study. However, a portion of the subjects recruited will have the CAPSIT-PD protocol exclusively for this study and not as a part of routine clinical care. "Wearing-off" and the "off-motor state" in PD are defined as a generally predictable recurrence of motor and non-motor symptoms as the effect of dopaminergic medications stops.(12) Subjects will temporarily stop all dopaminergic medications for a minimum of 12-hours in order to be assessed in the “off” motor state in the morning. (Most individuals with PD do not take medications overnight and usually take their last dose between 5-9pm. Therefore most participants will only be off medications for a few hours more than they normally would be as the study will be conducted in the morning) The on- and off-state assessments are listed below. Subjects will then take their usual morning dopaminergic medications and after one hour, to allow them to return to their best "on" state, repeat the CAPSIT-PD on-off battery. In addition to the on-off testing battery, several PD-related clinical features will be assessed, only in the on-state, using instruments recommended by the National Institute of Neurological Disorders and Stroke Common Data Element Project (NINDS-CDE)(24) for PD.

##### CAPSIT-PD on- and off-state testing battery

Each assessment will be conducted twice, once in the off-state and once after resuming PD meds in the on-state

1. Anxiety: Hamilton Anxiety Rating Scale (HAM-A)(25)
2. Depression: 17-item Hamilton Depression Rating Scale (HAM-D)(26)
3. Motor and non-motor fluctuations: 19-symptom wearing-off questionnaire (WOQ-19)(27)
4. Physical Disability: Schwab and England Scale (SE)(28)
5. Motor symptom severity: MDS-UPDRS part III(30)
6. Symbol Digit Modalities Test(45)
7. Stroop Color and Word Test(46)

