##### NINDS-CDE Recommended Assessments for PD-Specific Clinical Features (only for on-state)

1. Demographics
2. PD Medical History
3. PD Family History
4. PD and Non-PD Medication Log
5. Motor: MDS-UPDRS parts I-IV
6. Psychiatric: Structured clinical interview for DSM-IV-TR (SCID) axis I disorders, research version, non-patient edition (29)
7. Cognitive: Montreal Cognitive Assessment (MoCA)(31)
8. Other non-motor: Non-motor Symptoms Questionnaire (NMS-Quest)(35) and the Scales for Outcomes in Parkinson's disease autonomic dysfunction scale (SCOPA-AUT)(32,33)
9. Quality of life: 8-item Parkinson's Disease Questionnaire (PDQ-8)(34)
10. Questionnaire for Impulsive-Compulsive Disorders in Parkinson's Disease(QUIP)(47)

11. Neo Five-Factor Inventory(48)

12. Rapid Assessment of Physical Activity(RAPA)(49)

For objective 2:

The intervention will be 8 weeks in duration and include a 4-week dosage titration period and a 4-week maintenance period. Transdermal patch. Dosing will begin at baseline on day zero with either 1) placebo or 2) rotigotine at 2mg/24h and will be increased following the recommended dose escalation schedule for PD such that subjects will increase to 4mg/24hrs in week 2, and 6mg/24hrs in week 3. This dose of rotigotine is within the range shown to be safe and efficacious for the treatment of motor symptoms. 17,36,37) The timing of assessments is shown in Table 1. All assessments except for the physical exam, and the Clinical Global Impression for Anxiety Severity and change scales (CGI-S and CGI-C)(38) are part of the CAPSIT-PD on- and off-state testing battery, the table indicates administration points. Safety and tolerability will be assessed by recording adverse events.

b. Study duration and number of study visits required of research participants.

Objective 1 is one 3-hour cross-sectional visit, duration and visits for objective 2 are in Table 1

Table 1. Assessment schedule for objective 2					
Visit Number	Screening	Baseline	Follow-up visits		
Time	- - -	0	WK2	WK4	WK8: FINAL
Diagnostic Interview or AIM 1 Battery	X				X
Physical Examination	X				X
MDS-UPDRS I-IV	X				X
MoCA	X				X
CGI-Severity	X	X			
CGI-Change			X	X	X
HAM-A	X	X	X	X	X
HAM-D	X	X	X	X	X
SCOPA-AUT, NMS	X	X	X	X	X

c. Blinding, including justification for blinding or not blinding the trial, if applicable.

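### Objective 1 takes clustering of anxiety with motor fluctuations as evidence, but its only fluctuation indicator, the WOQ-19, also covers non-motor symptoms, so the clustering cannot be read as motor-specific

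*Combined protocol and SAP*

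**What the plan says.** Section 2, objective 1, sets out what will count as evidence: a demonstration that "both anxiety and motor fluctuations are increased in hypodopaminergic states and cluster together based on a latent variable will support this hypothesis". The rule has two parts, an increase of both features off medication and their clustering, and it speaks of motor fluctuations.

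Section 7c fits a latent profile analysis to eight variables: age of PD onset and "LEDD, HAMA, HAM-D, WOQ-19, SE, UPDRS part III, and MoCA score". These are "measured in the on-state) as latent profile indicators". HAM-A and WOQ-19 thus enter the same model as separate indicators.

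The on/off battery in section 4a describes the WOQ-19 as "Motor and non-motor fluctuations: 19-symptom wearing-off questionnaire (WOQ-19"). No other item in that battery is labelled as a fluctuation measure.

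Section 3 (Background) states that "Anxiety is one of the most common non-motor symptoms in PD". It defines wearing-off as a "generally predictable recurrence of motor and non-motor symptoms as the effect of dopaminergic treatment declines over a given dose", and says that in the most common atypical presentation "anxiety occurs as an episodic symptom potentially related to the wearing-off of dopaminergic treatment and motor fluctuations".

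Section 7c then lists predictors of profile membership: age, gender, on/off change scores and motor fluctuations. It names no instrument for the last. Nothing in the document provides for a motor-only WOQ-19 score, for setting aside items that overlap with anxiety, or for a profile model without the WOQ-19.

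**The concern.** The claim to be tested is about motor fluctuations, but the variable that stands for them is a mixed motor and non-motor score. By the plan's own account anxiety is a leading non-motor symptom and can be part of wearing-off. If some WOQ-19 items record anxiety, or symptoms that move with it, HAM-A and WOQ-19 share content and tend to be high in the same people even where anxiety and motor fluctuation are unrelated.

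What is at stake is the reading of the fitted profiles. A class with high HAM-A and high WOQ-19 would be taken as anxiety clustering with motor fluctuation. The mixed score cannot separate that from fluctuating non-motor symptoms without a motor component. The Background section also names a rival account, in which anxiety mimics autonomic dysfunction, itself a non-motor symptom. If the WOQ-19 picks up autonomic symptoms, that account could produce the same profile.

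**Working it through.** The plan gives no figure on this point to reproduce, so the check has two parts.

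**1. The text**

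| Step | Place | Content |
|---|---|---|
| Evidence rule | Section 2, objective 1 | Anxiety clusters with *motor* fluctuations |
| Indicators | Section 7c | HAM-A and WOQ-19 in one model, on-state values |
| WOQ-19 content | Section 4a battery | Motor *and* non-motor |
| Place of anxiety | Section 3 | A leading non-motor symptom; may occur with wearing-off |
| Safeguard | None found | No motor-only score, no run without WOQ-19 |

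Each link is in the document. What is missing is the item list, so the amount of overlap cannot be calculated.

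**2. Illustration of size**

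All inputs here are assumptions except n = 200 (section 2) and the 19 items (section 4a). Take two independent traits, anxiety and motor fluctuation. Of 19 yes/no items, k depend on anxiety and 19 − k on motor fluctuation, with logistic slopes of 1.0 to 2.0. The anxiety scale correlates 0.9 with the anxiety trait. The true association between anxiety and motor fluctuation is zero. The chance of a two-sided 5% result uses Fisher's transformation:

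z = atanh(r) × √(200 − 3); chance = Φ(z − 1.96) + Φ(−z − 1.96)

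Example, k = 3 and slope 1.5: r = 0.147, z = 0.148 × 14.04 = 2.08, chance about 0.54.

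| Items driven by anxiety (k) | Correlation of WOQ-19 total with anxiety scale | Chance of significance at n = 200 |
|---|---|---|
| 0 | about 0.00 | 5% |
| 1 | 0.04–0.05 | 9–10% |
| 2 | 0.09–0.10 | 24–27% |
| 3 | 0.14–0.15 | 53–56% |
| 5 | 0.25–0.27 | 94–97% |
| 8 | 0.43–0.47 | about 100% |

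The plan runs no pairwise test, so the table shows only how fast overlap can build up. For the planned type of model (eight indicators, three profiles, n = 200, anxiety and motor fluctuation independent, other loadings assumed), the mean WOQ-19 in the profile with the highest HAM-A was +0.04 SD with no overlap. It was +0.33 SD when non-motor items made up 20% of WOQ-19 variance and +0.49 SD at 50%, with those items assumed to correlate 0.5 with HAM-A. Under those assumptions the overlap reaches the profile means that the plan will interpret.

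**The case against.** The case on the other side has four parts.

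*The rule has a second condition.* Both features must also increase in the hypodopaminergic state, and the on/off battery includes MDS-UPDRS part III, a motor measure without this overlap. This stands, and it confines the point to clustering. The protection is partial: the WOQ-19 is also given in both states, so its change score has the same mixed content, and part III is labelled motor severity, not fluctuation.

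*The indicators are on-state values.* A reader might infer that a person whose anxiety alone comes and goes will score high on both scales. Anxiety that appears as medication wears off would tend to be low on an on-state HAM-A, so that example is weak. The on-state rule may reduce the overlap, but it does not make the WOQ-19 a motor measure.

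*A dopamine-linked anxiety without motor change could still fit the broader hypothesis.* Section 2 proposes a shared cause for certain anxiety syndromes and PD, and the plan deliberately defines wearing-off broadly. That is fair, but the stated evidence names motor fluctuations, and a mixed score cannot show which of the two was found.

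*Overlap alone rarely creates a profile.* With eight normal indicators at n = 200 and only one pair correlated, BIC preferred two profiles over one in 0 of 60 runs at r = 0.22 and in 4 of 60 at r = 0.35. This stands for isolated overlap. The actual indicators are likely to be intercorrelated; profiles can then form for other reasons, and overlap shifts their means.

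**Conclusion.** The mismatch between the motor claim and the mixed indicator is in the document and is not handled. A profile high on HAM-A and WOQ-19 would not by itself show a link to motor fluctuations. The point applies to the clustering part of the support rule and to any use of the WOQ-19 as the unnamed motor-fluctuation predictor. In that use the WOQ-19 would be both indicator and predictor.

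A reader might go further and call this a built-in false positive for objective 1. The documents do not support that, because the off-state increase is a separate condition with partly separate evidence. A reader might also attach a definite size. With non-motor shares of 20% to 50% and a correlation of 0.5 with HAM-A, √0.2 × 0.5 = 0.22 and √0.5 × 0.5 = 0.35. Those inputs have no source in the document, they assume that the whole non-motor block follows anxiety, and any p-value drawn from them belongs to a test that the plan does not run.

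The size is unknown: negligible if one item overlaps, substantial if several do. This is a cheap improvement, not a defect that invalidates the objective.

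**What to change.** Before the analysis, state in section 7c:

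1. The motor-fluctuation claim rests on a pre-specified WOQ-19 motor-item score, with the items listed. It replaces the WOQ-19 total as profile indicator and is the named measure wherever motor fluctuations predict membership.
2. The WOQ-19 non-motor items are reported separately and do not count towards the motor claim.
3. The profile model is refitted without the WOQ-19 as a sensitivity analysis. In that refit the motor-item score is no longer an indicator, so its use as a predictor of membership is not circular.

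MDS-UPDRS part IV is already collected ("Motor: MDS-UPDRS parts I-IV"), but the document does not describe its content. It could serve instead of the WOQ-19 motor items only if the sponsor confirms that it measures motor fluctuations.

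The cost is wording and one extra model fit, with no new data or visits. The motor-item score is narrower and somewhat less reliable than the 19-symptom total, so a true motor link may be harder to see.
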